- 3. How many subjects will be enrolled at all sites? 90- prospective, 45-retrospective (UVA only)
- **4.** How many subjects will sign a consent form under this UVa protocol? Between Jordan-Young Institute and UVA up to 90 subjects will sign consent for the prospective portion of the study—N=55 at UVA. 45

Page 5 of 41

subjects will sign a consent form for the retrospective portion of the study at UVA only. Total of 100 subjects will sign a consent form under this UVA protocol.

5. Provide an estimated time line for the study.

Enrolled subjects will be followed for 2 years post-surgery, or up until 2 years post-operatively for those who enter the study after surgery. We expect 50% enrollment to be achieved within one year, and 100% in two years. We would anticipate completion of follow up to occur in four years.

Inclusion/Exclusion Criteria

INSTRUCTIONS:

The inclusion and exclusion criteria should be written in bullet format.

If this is a collection of only retrospective* specimens or data, the inclusion criteria must include a start and stop date for when specimens/ data will be collected.

The stop date must be prior to the version date of this protocol.

*Retrospective: all specimens are in a lab at the time this protocol is approved by the IRB. All data exists in medical records or records from previous studies at the time this protocol is approved by the IRB.

1. List the criteria for inclusion

- Age at time of randomization or initial surgery: 16 50 years (skeletally mature)
- Primary, uncomplicated ACL reconstruction
- Autograft (STG or BPTB)

2. List the criteria for exclusion

- Multiple ligament knee injury (full thickness)
- Revision ACL reconstruction
- ACL reconstruction with allograft
- Meniscectomy > 75%
- Treatable articular cartilage lesions (debridement acceptable)
- Diagnosis of tibiofemoral or patellofemoral osteoarthritis (Kellgren Lawrence grade > II)
- Valgus knee alignment (weight bearing line outside of joint center)
- Prior ligament reconstruction of cartilage repair surgery in either ankle, knee, or hip
- Prior arthroscopic debridement surgery in either ankle, knee, or hip within 12 months
- Clinical evidence of hip disease
- Patellofemoral joint instability
- Significant patellar or tibiofemoral mal-alignment
- BMI > 35
- Type 1 Diabetes Mellitus
- Known connective tissue disorder (e.g. Ehlers-Danlos)
- Peripheral neuropathy
- Neurovascular/ circulatory disorder

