- Any form of inflammatory arthritis (e.g. RA, gout, pseudogout, lupus, etc.)

Page 6 of 41

- Significant co-morbid conditions as determined by the investigator (e.g. malignancy, renal, hepatic disease, etc.)
- Known or suspected psychological disorder
- 3. List any restrictions on use of other drugs or treatments. N/A

Statistical Considerations

1. **Is stratification/randomization involved?** Yes.

► IF YES, describe the stratification/ randomization scheme.

Block randomization will be completed *a priori* via a random number generator. 20 subjects will be allocated to group within each block (10 per group). Group assignments will be sealed in an opaque envelope each containing a number from 001-090. Each subject will be randomly assigned in a 1:1 ratio to receive one of the treatments (group) described below. Randomization envelope #001 will be used for the first subject, #002 for the second and so on. Group assignment for enrolled subjects will be determined intra-operatively. Prior to the determination of group assignment, the treating surgeon will drill two tibial tunnel guide pins, assessing pin placement via fluoroscopy, to ensure that one tunnel is anterior and the other is posterior to the 35% line. The sealed envelope will then be opened following confirmation of guide pin placement, and the procedure will be performed in accordance with the randomized group assignment.

Patients with a prior history of ACL reconstruction who enter the study post-operatively will be assigned to the appropriate group based on graft placement (anterior or posterior) that was performed for clinical care.

► IF YES, who will generate the randomization scheme?

X Other: Study coordinator

2. What are the statistical considerations for the protocol?

We have designed the study in a way that will make it easy to match an appropriate statistical procedure to test our primary hypotheses. Subjective and objective measures of knee function will be evaluated at 6, 12 and 24 months post-surgery.

3. Provide a justification for the sample size used in this protocol.

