Sample size for IKDC and KT-1000 side-side differences are calculated based on the expected between-group differences observed at the final time point of this study – 24 months post reconstruction. In order to observe a 2.4 mm between group differences in joint laxity symmetry, we need 40 patients per group. This estimate accounts for up to 3.5 mm in variability in KT-1000 side-side measurement change from pre-post-surgery. Further, we need 55 patients per group to detect a 8-point difference in IKDC score between groups assuming variability of 12 points in IKDC score. These estimates account for 20% attrition. Estimates are calculated to find statistically significant differences allowing for 5% type I error rate and power exceeding 80%.

4. What is your plan for primary variable analysis?

We will use independent t tests to determine group differences at each time point.

Page 7 of 41

5. What is your plan for secondary variable analysis?

We do not plan to use a secondary variable analysis.

6. Have you been working with a statistician in designing this protocol? Yes **IF YES, what is their name?** [name]

Page 8 of 41

- 7. Will data from multiple sites be combined during analysis? Yes
 - 7(a). Does the study involve randomization? Yes

IF YES, will randomization be done at each site or among sites? Randomization will be done at each site.

- 7(b). Has the sample size calculation considered the variation among sites? Yes
- 7(c). When combining the data from multiple sites to assess the study results, is the effect of the treatment to be tested (or the association to be tested) assumed to be the same across sites or vary among sites? What is the modelling strategy?

Yes. The effect of the treatment (placement of tibial tunnel) will be assessed using standard measures of joint laxity and patient-reported function. We have no evidence to believe that these outcomes differ between sites under standard protocols.

7(d). Is there a common protocol used in all sites? NO

IF NO, how will differences among sites, such as those related to the implementation, inclusion criteria, patient characteristics, or other sites characteristics, be considered to assess the study results?

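### The plan describes one sequential 001-090 envelope run and also randomisation at each site; it should specify a blocked list per site and put site in the primary analysis.

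*Combined protocol and SAP*

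**What the plan says.** Statistical Considerations item 1 sets out a single scheme. On blocks: "20 subjects will be allocated to group within each block (10 per group". On envelopes: "Group assignments will be sealed in an opaque envelope each containing a number from 001-090". On order of use: "Randomization envelope #001 will be used for the first subject, #002 for the second and so on". The ratio is 1:1. The item asks for any stratification, and none is named; no envelope range or prefix is tied to a site.

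The Human Participants section gives total enrolment as "90- prospective, 45-retrospective (UVA only", and its item 4 puts 55 of the 90 prospective patients at UVA. The envelope run therefore has the same length as the two-site prospective total.

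Item 7(a) asks whether randomisation is within or across sites. The answer is "Randomization will be done at each site".

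On the handling of site:
- Item 4 plans independent t tests at each time point, with no site term.
- Item 7(b) reads "Has the sample size calculation considered the variation among sites? Yes", but the sample-size justification in item 3 lists only a difference, a variability, attrition, type I error and power.
- Item 7(c) asks for a modelling strategy and gives none; it says there is no evidence that outcomes differ between sites.
- Item 7(d) reads "Is there a common protocol used in all sites? NO". Its explanation says enrolment criteria are the same and leaves adjustment for patient characteristics to unspecified steps after data collection.

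**The concern.** A coordinator cannot tell from this text which envelope the second site's first patient receives. It could be the next number in a common series, the first of a reserved range, or the first of a separate list. These options differ in how well the arms are balanced within each site.

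Balance within site matters because the plan itself says the sites do not share a protocol, so surgical or measurement practice could differ between them. If one arm happens to draw more of its patients from one site, part of any site difference enters the tunnel comparison, and the planned t test does not remove it. If randomisation really is by site, an analysis that ignores site leaves between-site variation in the error term and gives up some precision.

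**Working it through.** **Inputs from the documents.** Block size 20, 10 per group; envelopes 001-090; prospective enrolment 90, of which 55 at UVA; target to complete 75; attrition 20%; IKDC variability 12 points; IKDC target difference 8 points.

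**Inputs derived or assumed.** Second site 90 - 55 = 35. Patients from the two sites arrive in random order (assumed). IKDC difference between sites 3 to 8 points (assumed; the documents give none). The 12 points are taken as the within-site SD.

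**The plan's own figure.** 75 x 1.2 = 90, so the envelope run is sized to the whole two-site prospective enrolment, not to one site.

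**Reading A: one shared run used in order at both sites.** Simulation of 200,000 trials: blocks of 20, first 90 allocations, split at random 55/35.

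| | UVA (55) | Second site (35) |
|---|---|---|
| Mean absolute arm difference | 3.9 | 3.8 |
| 95th percentile | 9 | 9 |
| More than 5 | 21% | 20% |
| 9 or more | about 10% | about 9% |
| Largest simulated | 21 | 21 |

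**Reading B: a separate list in blocks of 20 at each site.** 55 = 2 x 20 + 15 and 35 = 1 x 20 + 15, so only a part block of 15 can be unbalanced. With k of the 15 in one arm, P(k) = C(10,k) C(10,15-k) / C(20,15), and C(20,15) = 15,504.
- k = 5 or 10 (difference 5): 2 x 252 / 15,504 = 3.3%
- k = 6 or 9 (difference 3): 2 x 2,100 / 15,504 = 27.1%
- k = 7 or 8 (difference 1): 2 x 5,400 / 15,504 = 69.7%
- Mean difference: 2 x (252 x 5 + 2,100 x 3 + 5,400 x 1) / 15,504 = 25,920 / 15,504 = 1.67

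The difference cannot exceed 5 at either site for the planned split. It could reach 10 only if a site stopped halfway through a block, for example at 30 or 50.

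**Reading C: one run cut into 001-055 and 056-090.** At most 5 at UVA. At the second site the mean is 2.5 and the largest simulated value is 13, because its range starts partway through a block.

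**Effect on the comparison under reading A.** The share of patients from UVA differs between arms by 0.08 on average and by 0.20 at the 95th percentile. Multiplied by the assumed site difference:
- Typical shift: 0.08 x 3 = 0.24 to 0.08 x 8 = 0.64 IKDC points
- 95th percentile: 0.20 x 3 = 0.6 to 0.20 x 8 = 1.6 IKDC points, against a target of 8

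**Effect on the standard error under reading B.** Leaving site out adds p(1-p)D² to the variance, where p = 55/90 = 0.611, p(1-p) = 0.238 and D is the site difference.
- D = 3: 0.238 x 9 = 2.1; sqrt(1 + 2.1/144) = 1.007, about 1% too large
- D = 8: 0.238 x 64 = 15.2; sqrt(1 + 15.2/144) = 1.051, about 5% too large

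**The case against.** **The two statements may not conflict.** The answer in 7(a) could mean only that envelopes are opened locally, from a shared or divided set. That is possible but not written, and readings A and C leave within-site balance less well controlled than reading B. The need to specify stands.

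**Per-site randomisation would work.** A reader might infer that neither scheme secures balance within site. The documents do not support that: separate lists in the plan's own blocks of 20 hold the difference to 5. The per-site scheme is unspecified, not defective.

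**Block size.** A reader might also count it as an error that 20 divides none of 90, 55 or 35. An incomplete last block is routine, and because 55 and 35 are odd, no even block size would end exactly there.

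**Validity of the test.** It is tempting to say that ignoring site makes the standard error wrong in a way that threatens the type I error. Under stratified randomisation it is too large, so the test is conservative. Under a shared run the imbalance is due to chance in a valid randomisation, not systematic bias.

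**Sites may be alike.** Enrolment criteria and the prescribed rehabilitation programme are stated to be the same, and 7(c) sees no evidence of site differences. This limits the likely size of the problem. It does not cover surgical or measurement practice, and 7(d) still answers that there is no common protocol.

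**Item 7(b) may be true.** Site variation could have been considered and judged negligible. The documents support only the statement that no site quantity is described in the sample-size justification.

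**Conclusion.** The concern holds as an unresolved inconsistency in the randomisation scheme, together with an analysis that omits the factor by which the plan says it randomises. A shared run would leave arm differences averaging 3.8 to 3.9 patients within a site, and 9 or more in about 9-10% of trials at a given site; separate site lists would cap them at 5. These figures rest on the 55/35 split (35 by subtraction) and, for the shared run, on random arrival order.

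The consequence for the estimate is modest. For assumed site differences of 3-8 IKDC points, the 95th percentile shift under a shared run is 0.6 to 1.6 points against a target of 8, and the loss of precision under per-site randomisation is about 1-5%. The reason to act is that the gap is real and nearly free to close, not that the trial's conclusions are in jeopardy.

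**What to change.** 1. **Item 1 and 7(a):** state that each site has its own blocked list and its own envelope series, numbered separately. Blocks of 20 suffice for balance at the planned split. Smaller mixed blocks are optional; they tighten balance but make allocation slightly more predictable.
2. **Item 4:** for the randomised comparison, replace the unadjusted t test with a linear model with group and site as fixed effects, specified now and not left until after data collection.
3. **Item 7(b):** reword to say that the sample-size justification includes no site quantity, with the reason if site variation was judged negligible.
4. **If envelopes have already been opened:** apply the site lists only to the unused ones. This abandons any open block, so the bound of 5 will not hold for the whole trial. The site term in the model still applies.

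The cost is one model term, regenerated unused envelopes and a few lines of text. No extra patients are needed.

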This study is designed as a prospective, double arm, study. Patients with a diagnosed rupture of the anterior cruciate ligament (ACL) who are scheduled for surgical reconstruction will be considered for enrollment. Eligible subjects will be allocated to one of two groups based on the location of the tibial tunnel (anterior vs. posterior) during the surgical procedure. The study population will consist of patients 16-50 years of age, with ACL rupture, who are seeking surgical reconstruction. Patients with active infection, previous ACL surgery, multiple ligament knee injury, previous joint modifying surgery in target knee within 12 months of planned procedure, flexion contracture, valgus alignment, pathologic ligament instability, knee osteoarthritis, inflammatory joint disease, metabolic bone disease (marked bone loss or moderate to severe osteoporosis), comorbidities such as type 1 diabetes, connective tissue disorder, or morbid obesity (BMI ≥35) will be excluded.

Subjects will return for follow-up visits at 6, 12, and 24 months post-surgery. If a subject is unable to come to UVA for a follow up visit, a home visit can be arranged with a member of the study team. Note that all data cannot be collected through a home visit, but instead only the subjective outcomes and some aspects of the knee exam can be collected. Follow up will be completed at 24 months for all enrolled subjects. Additionally, subjects with a prior ACL reconstruction who meet all study criteria, may enter the study at any post-operative time point (retrospective aspect of the study).

The primary objective of this study is to collect data on subjective and objective measures of knee related function in subjects with an anterior vs. posterior placed tibial tunnel through 24 months postoperative follow-up.

The primary analysis will compare groups at 24-months post-op with regard to:

- 1. Clinically significant difference of at least 8 points on IKDC score
- 2. Clinically significant difference of at least 2.4 mm knee joint laxity (KT-1000)

Background

1. Provide the scientific background, rationale and relevance of this project.

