Although extensive research has been carried out on ACL Femoral Tunnel placement, very little attention has been given to the tibial tunnel. Staubli et al. suggest that the tibial tunnel be placed in the center of the ACL footprint, which they described as being approximately 43% of the way (anterior to posterior) across the proximal tibia at its widest extent. However, others have suggested that a more anterior placement may yield improved biomechanical and clinical results. The center of the ACL footprint and the posterior aspect of the anterior horn of the lateral meniscus does not yield tibial tunnel placement a consistent percentage of the way across the tibial plateau⁴, therefore, guidelines should be based on intraoperative fluoroscopic measurements. However, the question remaining is what percentage of the A-P distance across the tibia is the ideal location for the tibial tunnel in ACL reconstruction. This study will help answer that question.

Page 4 of 41

Hypothesis to be Tested

Objective:

Compare anterior versus posterior tibial tunnel placement for ACL reconstruction in a prospective randomized clinical trial.

Hypotheses:

A more anterior placed tibial tunnel will yield improved outcomes with regard to:

- 1. Improved knee-specific self-reported function (IKDC)
- 2. Decreased knee joint laxity (KT-1000)

Study Design: Biomedical

- 1. Will controls be used? No
- 2. What is the study design?

Single-blind, randomized controlled clinical trial

3. Does the study involve a placebo? No

Human Participants

Ages: 16-50

Sex: Male and Female

Race: All

Subjects- see below

INSTRUCTIONS: For question 1-4 below insert an exact #. Ranges or OPEN is not allowed. This # should be the maximum # you expect to need to enroll (i.e. sign consent) If you are only collecting specimens the number of participants should equate to the # of specimens you need. If you are collecting only data from a chart review the number should designate the number of subjects whose medical records you plan to review. Age/ Sex/Race criteria should designate the demographics of participants from whom you will obtain the specimen/data.

- **1.** Provide target # of subjects (at all sites) needed to complete protocol.75(prospective aspect) 45 for retrospectice (UVA only)
- 2. Describe expected rate of screen failure/ dropouts/withdrawals from all sites.

We expect up to a 20% rate of attrition due to loss of follow up.

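### The primary analysis set is not named, although up to 45 non-randomised patients carry the same group labels as up to 90 randomised ones

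*Combined protocol and SAP*

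**What the plan says.** All references are to the combined protocol and SAP.

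- **Allocation of prospective patients** (Statistical Considerations, item 1): 1:1 randomisation with sealed envelopes numbered 001 to 090.
- **Allocation of post-operative entrants** (same item, next paragraph): they "will be assigned to the appropriate group based on graft placement (anterior or posterior) that was performed for clinical care". The study summary says that such patients "may enter the study at any post-operative time point (retrospective aspect of the study".
- **Numbers** (Human Participants, items 1 and 3): the target is "75(prospective aspect) 45 for retrospectice (UVA only") and enrolment is "90- prospective, 45-retrospective (UVA only").
- **Primary objective** (study summary): to collect "measures of knee related function in subjects with an anterior vs. posterior placed tibial tunnel through 24 months postoperative follow-up". The primary analysis then compares the groups at 24 months on IKDC and KT-1000.
- **Objective** (Hypothesis to be Tested): "Compare anterior versus posterior tibial tunnel placement for ACL reconstruction in a prospective randomized clinical trial".
- **Analysis** (Statistical Considerations, items 4 and 5): "We will use independent t tests to determine group differences at each time point" and "We do not plan to use a secondary variable analysis".
- **Sample size** (Statistical Considerations, item 3): 40 per group for a 2.4 mm KT-1000 difference with variability of 3.5 mm, and 55 per group for an 8-point IKDC difference with variability of 12 points. Both are said to allow for 20% attrition, with 5% type I error and power above 80%.
- **Adjustment** (Statistical Considerations, item 7(d)): differences in patient characteristics are to be accounted for after data collection is complete. No covariate or model is given, and the question being answered is about sites.

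**The concern.** Both cohorts end up in groups called anterior and posterior, and the rule that places the non-randomised patients there sits inside the description of the randomisation scheme. An analyst told to compare the groups by t test finds no instruction to leave those patients out.

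If they are included, a comparison presented as randomised becomes partly observational. Whatever led surgeons to one placement or the other in past care enters the estimate, with no prespecified adjustment. If they are left out, that is also a decision the plan does not record. In either case the set can be chosen once both results are visible. The choice matters for power as well: on the plan's inputs, IKDC power is about 80% without the retrospective patients and about 93% with them.

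**Working it through.** **1. Inputs.** From the protocol: IKDC difference 8, SD 12; KT-1000 difference 2.4 mm, SD 3.5 mm; 5% type I error; power above 80%; 20% attrition; 90 randomised and 45 retrospective. Assumed: two-sided tests (sidedness is not stated), and equal groups unless noted.

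**2. The plan's own sample sizes.** Per group, n = 2(1.96 + 0.8416)² × (SD/difference)².

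- IKDC: 15.70 × (12/8)² = 35.3, so 36; 36/0.8 = 45. The t-based value is 36.3, so 37; 37/0.8 = 46.25, so 47. The stated 55 is not reproduced at 80% power. It leaves 55 × 0.8 = 44 evaluable, with t-test power of 87.1%. That is consistent with power above 80%, so 55 is not shown to be wrong.
- KT-1000: 15.70 × (3.5/2.4)² = 33.4, so 34; 34/0.8 = 42.5, so 43. Multiplying by 1.2 instead gives 40.8, so 41, close to the stated 40.

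**3. Stated need against envelopes.** IKDC: 2 × 55 = 110, which is 20 more than 90. KT-1000: 2 × 40 = 80, which fits within 90.

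**4. Share of non-randomised patients.** 45/(90 + 45) = 33%.

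**5. Power with randomised patients only.** 90 × 0.8 = 72 completers, or 36 per group.

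| Set | IKDC, t test | KT-1000, t test |
|---|---|---|
| 36 + 36 (90 less 20%) | 79.7% | 81.8% |
| 40 + 32 (same total, uneven loss) | 79.2% | 81.4% |
| 75 in all (stated target) | 81.3% | 83.4% |
| Pooled, 54 + 54 (20% loss in both cohorts, even split) | 93.0% | 94.2% |

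The normal approximation at 36 per group gives 80.7% for IKDC, but the planned test is a t test. The target of 75 also does not follow from 90 with 20% loss, which leaves 72.

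**6. Precision.** The standard error is SD × √(2/n per group).

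- Randomised only, 36 per group: IKDC 12 × √(2/36) = 2.83; KT-1000 3.5 × √(2/36) = 0.82 mm.
- Pooled 72 + 36 (54 per group): 2.31 and 0.67 mm.
- Pooled 72 + 45 (58.5 per group): 2.22 and 0.65 mm.

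**7. Sensitivity under pooling (illustration only).** Assume no true effect, an even split, and a confounded IKDC difference B between placements within the retrospective cohort. The pooled estimate shifts by B × (retrospective share), where the share is 36/108 = 0.333 or 45/117 = 0.385.

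| B (points) | Shift | Two-sided type I error |
|---|---|---|
| 0 | 0 | 5% |
| 2 | 0.67 to 0.77 | 5.9% to 6.4% |
| 3 | 1.00 to 1.15 | 7.1% to 8.1% |
| 5 | 1.67 to 1.92 | 11.0% to 13.8% |

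The values of B are invented to show sensitivity; the protocol gives no figure for them.

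**The case against.** The strongest reply is that a randomised-only analysis is already implied. The hypotheses sit under an objective that names a randomised trial, the design is given as a single-blind randomised controlled trial, item 2 of Statistical Considerations ties the statistical procedure to those hypotheses, and the two cohorts are counted separately throughout. This stands as evidence of likely intent, and it makes the gap one of wording. It does not define the set: the primary objective in the summary covers any subject with either tunnel position, and the randomisation section gives the retrospective patients the same groups.

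Four stronger readings are tempting, and the documents support none of them:

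- **That pooling is planned, and that 110 exceeding 90 shows it.** No section states pooling. The KT-1000 figure of 80 fits within 90, and the plan's IKDC inputs at 80% power need only 45 to 47 per group. The excess is a separate inconsistency.
- **That item 5 rules out any analysis of the retrospective cohort.** That item concerns secondary variables, not populations. It is still true that no section gives the cohort an analysis of its own.
- **That no adjustment is planned.** Item 7(d) offers some. It is unspecified, deferred until after data collection and given in answer to a question about sites, so the accurate statement is that none is prespecified.
- **That the type I error is inflated.** The range of about 6% to 14% depends on pooling occurring and on assumed confounding. The documents give no evidence that past placement was related to prognosis.

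**Conclusion.** The concern holds as an omission. The only planned test has no named population, and up to a third of enrolled patients are non-randomised members of the groups it compares. This must be fixed because it decides who enters the primary comparison of a trial described as randomised. That conclusion rests on the missing definition alone and does not need the illustrative type I figures.

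The sample-size paragraph also needs correcting, since 110 patients cannot come from 90 envelopes. For the patients who will be randomised, IKDC power is 79.7% at 36 per group, just short of the plan's own criterion; KT-1000 meets it at 81.8%. These figures assume two-sided t tests, the plan's SDs and exactly 20% loss. An uneven loss lowers IKDC power slightly.

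**What to change.** 1. **Name the set.** State that the primary analysis set is the envelope-randomised patients, analysed as randomised. State that the retrospective cohort is not pooled in the primary test and is reported separately as observational. If that report is adjusted, name the covariates in advance; which ones is the sponsor's choice.
2. **Restate the sample size for the 90 randomised.** Replace the 55-per-group statement with power at 36 per group: 79.7% for IKDC, said plainly to be just under 80%, and 81.8% for KT-1000. Reconcile the target of 75 with the 72 that 20% attrition leaves.

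The cost is a sentence on the analysis set and a revised paragraph. Enrolment, envelopes and blocks stay as they are. What is given up is the apparent gain in precision from pooling shown above, on both endpoints.

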Potential subjects will be identified, screened, and eligibility criteria reviewed in a similar manner at each institution. Each practice will follow the same criteria for enrollment. Statistical considerations will be employed following the completion of data collection to account for differences in patient characteristics/ demographics.

Biomedical Research

1. What will be done in this protocol?

Study Procedures:

All procedures apply to subjects who enter the study prior to surgery.

Screening visit (Visit 1)

After written informed consent is obtained, initial screening will consist of a thorough medical history and physical examination. Special attention will be given to inclusion and exclusion criteria as listed above. Only patients who meet all inclusion and exclusion criteria will be allowed to continue to baseline outcomes data collection. The following subjective outcomes and clinical examination data will be collected at each session.

Subjective Outcomes (10 minutes)

- International Knee Documentation Committee (IKDC) Subjective Knee Evaluation
- Marx Activity Rating Scale

Page 9 of 41

X-ray (15 minutes)

Standing 2-view (posterior-anterior, lateral)

Clinical Evaluation (10 minutes)

- Knee joint laxity with KT-1000
- Knee joint range of motion
- Thigh circumference (15 cm above knee cap)

Surgery (Visit 2)

• Record surgical details: procedure(s) performed, time of procedure, tunnel diameter, tunnel placement details, other arthroscopic findings pertinent to case

Follow Up Visits (Visits 3-5)

Subjects who enter the study after surgery will complete the visits below based upon when they enter the study from their surgery date. If subjects are unable to come to UVA for the follow up visits, it is possible to arrange a home visit with a member of the study team to collect outcomes. Please note that we can only collect questionnaires and the KT-1000 ligament laxity measurement of the knee exam through a home visit.

- 6 months (approximately 182 ± 14 days following surgery)
 - Review of criteria for enrollment
 - Record adverse events
 - Clinical evaluation
 - KT-1000 Ligament Laxity Assessment Questionnaires
 - Marx Activity Scale
 - IKDC Subjective Questionnaire
- 12 months (approximately 364 ± 21 days following surgery)
 - Record adverse events
 - Standing 2-view (posterior-anterior, lateral) x-ray
 - Clinical evaluation
 - o KT-1000 Ligament Laxity Assessment
 - Questionnaires
 - Marx Activity Scale

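### The KT-1000 sample size uses the variability of pre-to-post change, but the stated test has no baseline term, and the 40 per group falls short of its own power target after attrition

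*Combined protocol and SAP*

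**What the plan says.** Statistical Considerations, item 3, sets the KT-1000 requirement: "In order to observe a 2.4 mm between group differences in joint laxity symmetry, we need 40 patients per group". Both sample sizes "are calculated based on the expected between-group differences observed at the final time point of this study", which is 24 months. The spread is given as a change: "This estimate accounts for up to 3.5 mm in variability in KT-1000 side-side measurement change from pre-post-surgery". Attrition and error rates follow: "These estimates account for 20% attrition", and the estimates are made "allowing for 5% type I error rate and power exceeding 80" percent. IKDC is sized in the same item at 55 per group, for 8 points and a variability of 12 points in the score.

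Item 4 gives the whole primary analysis: "We will use independent t tests to determine group differences at each time point". It names no dependent variable and no covariate. The protocol summary places the primary comparison at 24 months and lists KT-1000 laxity as one of its two outcomes.

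The screening visit records "Knee joint laxity with KT-1000" and IKDC before surgery. Patients who join after surgery complete only the follow-up visits that remain to them. The Human Participants section plans 90 prospective and 45 post-operative (retrospective) subjects.

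**The concern.** The SD of a pre-to-post change and the SD of a value at one visit are different quantities. They are linked by the pre-operative SD and the pre-post correlation, and the documents give neither. A t test on 24-month values depends on the second SD, while the plan supplies the first. For this primary outcome, the plan therefore does not establish the power of the test it states.

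A second question is whether the 40 meets the plan's own target if 3.5 mm is accepted as the right SD.

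**Working it through.** **Inputs.** From item 3: difference 2.4 mm; variability 3.5 mm (read as an SD, although the text does not use that term); 5% type I error; power above 80%; 20% attrition. From item 1: "Each subject will be randomly assigned in a 1:1 ratio". Two-sided testing is assumed, because the plan does not state sidedness.

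**Step 1. Reproduce the 40.** By the normal approximation, n = 2(1.96 + 0.84)² × (3.5/2.4)² = 2 × 7.849 × 2.127 = 33.4 evaluable per group. Multiplying by 1.2 gives 40.06, so the stated 40 is reproduced with the 3.5 mm change figure as the SD and attrition added as n × 1.2.

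**Step 2. Does 40 meet the stated target at SD 3.5?** To be left with n after 20% loss, one must enrol n/0.8.
- 40 × 0.8 = 32 completers per group. The standardised difference is 2.4/3.5 = 0.686, and t-test power is 77%.
- The t-test calculation needs 34.4, so 35 whole patients per group. Enrolment is 34.4/0.8 = 43. Rounding up to 35 before dividing gives 44.
- Planned enrolment is 90/2 = 45 per arm, leaving 45 × 0.8 = 36 completers. Power at SD 3.5 is 82%.

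**Step 3. What the change SD implies for the 24-month SD.** Let k be the ratio of pre-operative to 24-month SD and ρ the pre-post correlation. Then Var(change) = SD₂₄² × (1 + k² − 2ρk), so SD₂₄ = 3.5/√(1 + k² − 2ρk). Neither k nor ρ is in the documents, so the values below are assumptions that show a range. Power is for 36 per arm.

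| k | ρ | SD₂₄ (mm) | t-test power |
|---|---|---|---|
| 1 | 0 | 2.47 | 98% |
| 1 | 0.5 | 3.50 | 82% |
| 1 | 0.7 | 4.52 | 60% |
| 1 | 0.8 | 5.53 | 44% |
| 1.5 | 0 | 1.94 | 99.9% |
| 1.5 | 0.5 | 2.65 | 97% |
| 1.5 | 0.8 | 3.80 | 75% |
| 2 | 0.8 | 2.61 | 97% |

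With equal SDs, the stated figure transfers exactly at ρ = 0.5. Below that it is conservative, and above that it is too small. If the pre-operative spread is larger than the 24-month spread, much of the loss disappears.

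**Step 4. What baseline adjustment does.** The ANCOVA residual variance is the smallest value of Var(Y − bX) over all b, where Y is the 24-month value and X the pre-operative value. The change score is the case b = 1, so the residual SD cannot exceed the SD of change, whatever k and ρ are. With k = 1 the residual SD is SD₂₄ × √(1 − ρ²). At ρ = 0, 0.5 and 0.8 this is 2.47, 3.03 and 3.32 mm, with power of 98%, 91% and 86% at 36 per arm. If 3.5 mm is the SD of change, power at 36 per arm is about 82% or better.

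**The case against.** The strongest reply is that item 4 names no dependent variable. A t test on change from baseline at 24 months would also fit its wording, and then 3.5 mm would be the right SD. This stands in part: a reader might infer that the plan sized an analysis that will not be run, and the documents do not go that far. They show a stated test with no mention of change or baseline. If change was meant, the plan has to say so.

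A reader might also infer that the trial is underpowered for KT-1000, citing the 44% above. That is not supported. The figure needs a correlation of 0.8 and equal pre- and post-operative SDs together, and the documents offer neither. Equal SDs is a strong assumption when the first measurement is on a ruptured ligament and the second on a reconstructed one. At 36 per arm and SD 3.5, power is 82%. The plan also words 3.5 mm as a ceiling, which favours the sponsor.

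The 77% is a separate matter of how attrition was added. It does not arise from change versus value, and it does not describe the trial as planned, which has 45 per arm. It is still an error in the stated justification.

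IKDC asks for more patients than KT-1000, so the KT-1000 figure does not set the trial's size. However, 55 per group is not what will be enrolled, so the IKDC figure gives KT-1000 no extra margin.

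Finally, an unadjusted t test is valid in a randomised comparison. ANCOVA is recommended here because it makes the only SD in the plan usable, not because the t test is wrong.

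**Conclusion.** The concern holds as a mismatch of inputs. The KT-1000 spread is that of a pre-to-post change, while the stated test has no baseline term. The stated power applies to that test only if the 24-month SD is near 3.5 mm. The documents do not give this SD, and the error could lie in either direction.

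Separately, 40 per group does not deliver the power claimed for it: 32 completers give 77% at SD 3.5. About 43 enrolled are needed, and the planned 45 per arm exceed that, so enrolment need not change on this account.

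These results assume that 3.5 mm is an SD, that testing is two-sided, that attrition is 20%, and that the 90 prospective patients split equally. The matter should be corrected, but underpowering has not been demonstrated.

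**What to change.** 1. For the randomised patients, analyse the 24-month KT-1000 side-to-side difference by ANCOVA, with treatment group and the pre-operative side-to-side difference in the model.
2. State that 3.5 mm is the SD of change and is therefore an upper bound on the ANCOVA residual SD.
3. Restate the KT-1000 requirement as 43 per group including 20% attrition (34.4/0.8), or 44 if the evaluable number is first rounded up to 35.
4. Adjust IKDC for its pre-operative score as well. This is a gain in precision only: its 12-point variability is not described as a change SD, so the upper-bound argument does not apply to it.
5. Restrict the baseline-adjusted analysis to randomised patients. Report the post-operative entrants (45 planned) separately, because the study plans no pre-operative KT-1000 for them.

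If the unadjusted t test is kept, name its dependent variable. If that is the 24-month value, give its SD with a source and recompute the sample size.

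The cost is analysis-plan wording and one covariate per outcome, both already collected at screening. No added visit, measurement or enrolment is needed.
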